HbA _{1c}	X					X		X	X ^a	
Thyroid-stimulating hormone (TSH)	X									
Anti-alirocumab antibodies ^k			X	X		X		X	X ^l	
Library samples ^m			X ^d	X		X		X		
PK samples ^{k, n}			X	X		X	X	X		
			X							
			X							

- ^a To be obtained at the follow up visit only in case of clinically relevant abnormal values for these parameters(or clinically relevant abnormal finding for physical examination) at the end of double-blind treatment visit.
- ^b Injection training at screening period visit Week -1 is performed with placebo. Investigators will have the option of providing a second placebo for alirocumab for patients who require additional self-injection training prior to randomization, e.g. the patient or investigator may elect to have the patient inject at home or at the study site.
- ^c Injection training at randomization visit Week 0/Day 1 is performed at the site by the patient or a trained designated person with double-blind study treatment kit allocated by IVRS/IWRS. Further training with a double-blind treatment can be done between Week 0 and 4 and at additional scheduled or unscheduled visits, as per patient or investigator's judgment.
- ^d To be performed before randomization.
- ^e Along with kit dispensation, the treatment administration package should be given as well as the IMP diary and injection instruction manual, as needed.

- f* LDL-C will also be measured (via the beta-quantification method) at Week 0 and Week 24
- g* Hematology includes: complete blood cell count (CBC) including red blood cell distribution width (RDW) and reticulocyte count, hematocrit, hemoglobin (Hb), red blood cell count, white blood cell count with differential count and platelets. Chemistry includes: glucose, sodium, potassium, chloride, bicarbonate, calcium, phosphorous, urea nitrogen, creatinine, uric acid, lactate dehydrogenase (LDH), total protein, albumin, and gamma-glutamyl transferase (yGT).
- h* Liver panel: alanine aminotransferase (ALT), aspartate aminotransferase (AST), alkaline phosphatase (ALP) and total bilirubin.
- i* Positive HCV antibody results for the W24 assessment will be followed up with confirmatory test.
- j* Women of Child Bearing Potential (WOCBP) only.
- k* PK and anti-alirocumab antibodies collections are to be done prior to the IMP injection.

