10.1.3 Follow-Up Period

10.1.3.1 Follow-Up Visit (Visit 9/ Week 32/ Day 225 \pm 7)

- Collect AEs
- Record concomitant medication
- Get body weight measurement
- Take vital signs including HR and BP.
- Perform physical examination (only in case of clinically relevant abnormality at the end of treatment visit)
- IVRS/IWRS contact to document the end of study
- Urinalysis (only in case of clinically relevant abnormal value at the end of treatment visit)
- Urine pregnancy test (WOCBP only)
- Obtain fasting blood sample for:

- Anti-alirocumab antibodies (as per schedule note in study flowchart of [Section 1.2](#))
- Only in case of clinically relevant abnormal values for these parameters at the end of treatment visit will the following be obtained at this visit:
 - a) Hematology: CBC including RDW and reticulocyte count, hematocrit, Hb, red blood cell count, white blood cell count with differential blood count and platelet
 - b) Chemistry: glucose, sodium, potassium, chloride, bicarbonate, calcium, phosphorous, urea nitrogen, creatinine, uric acid, LDH, total protein, albumin and γ GT
 - c) HbA1c
 - d) Liver panel (ALT, AST, ALP, and total bilirubin)
 - e) CPK

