### ***Observation period***

The period of safety observation starts from the time when the patient gives informed consent and is divided into the following periods:

- The PRE-TREATMENT period: defined as the time from the signed informed consent up to the first dose of double-blind IMP;
- The treatment-emergent adverse event (TEAE) period: defined as the time from the first dose of double-blind IMP up to the day of last dose of double-blind IMP injection+70 days (10 weeks) as residual effect of alirocumab is possible until 10 weeks after the discontinuation of double-blind IMP injection.

The TEAE period will include:

- The TREATMENT period defined as the time from the first dose of double-blind IMP up to the day of last dose of double-blind IMP injection + 21 days, as serum concentration of alirocumab is expected to be  $>10 \mu\text{g/mL}$  for approximately 21 days following administration of 150 mg, and because throughout the previous studies it was observed that when alirocumab concentrations declined below this concentration, decrease in effect on LDL-C is observed.
- The RESIDUAL TREATMENT defined as the time from the day of last dose of double-blind IMP injection + 22 days up to the day of last dose of double-blind IMP injection + 70 days (10 weeks).
- The POST-TREATMENT period: defined as the time starting the day after the end of the TEAE period (ie, 71 days after the day of last dose of double-blind IMP injection).

The on-study observation period is defined as the time from the day of first dose of double-blind IMP (capsule or injection, whichever comes first) until the last protocol planned visit of the patient. The last protocol planned visit is defined as the follow-up visit if done, or else 32 weeks after the randomization of the patient.

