#### ***2.1.4.3 Laboratory safety variables***

Clinical laboratory data consists of blood analysis, including hematology, clinical chemistry, and urinalysis. Clinical laboratory values after conversion will be analyzed into standard international units and will be used in all listings and tables.

Unless otherwise specified, blood samples for clinical laboratories will be taken at Visit 1 (Week -3), Visit 3 (Week 0), Visit 6 (Week 12), Visit 8 (Week 24), or early termination, and

during the follow-up visit (Visit 9 [Week 32]) in case of abnormality unless otherwise specified. The laboratory parameters will be classified as follows:

- Hematology:
  - Red blood cells and platelets: hemoglobin, hematocrit, erythrocytes count, platelets count, reticulocyte count, red blood cell distribution width (RDW);
  - White blood cells: white blood cell count, neutrophils, lymphocytes, monocytes, basophils, eosinophils.
- Clinical chemistry:
  - Metabolism: glucose, total protein, albumin, creatine phosphokinase;
  - Electrolytes: sodium, potassium, chloride, calcium, phosphorus, bicarbonate;
  - Renal function: creatinine, eGFR, blood urea nitrogen, uric acid;
  - Liver function (also measured at Week 4, Week 8, and Week 16, except gamma glutamyl transferases [GGT] and lactate dehydrogenase [LDH]): ALT, aspartate aminotransferase (AST), alkaline phosphatase (ALP), GGT, total bilirubin, and in case of total bilirubin values above the normal range, must include direct and indirect bilirubin, LDH.
- Hepatitis screen: anti-hepatitis-C antibody (Ab) (at Week -3 and Week 24/or early termination).

Technical formulas are described in [Section 2.5.1](#).

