#### **2.4.5.3 Analyses of laboratory variables**

The summary statistics (including number, mean, median, first quartile (Q1), third quartile (Q3), standard deviation, minimum and maximum) of all laboratory variables (central laboratory values and changes from baseline) will be calculated for each visit or study assessment (baseline, each post-baseline time point, last on-treatment, worst on-treatment value) by treatment group. In addition, for some parameters of interest, mean changes from baseline with the corresponding SE could be plotted over time (at same time points) in each treatment group. This section will be organized by biological function as specified in [Section 2.1.4.3](#). For glucose, only fasting samples will be summarized.

The incidence of PCSAs (list provided in [Appendix A](#)), at any time during the TEAE period will be summarized by biological function and treatment group whatever the baseline level and/or according to the following baseline status categories:

- Normal/missing;
- Abnormal according to PCSA criterion or criteria.

Glucose (quantitative summary and PCSA) will also be analyzed, overall and according to the diabetic status at baseline.

For parameters for which no PCSA criteria are defined, similar table(s) using the normal range will be provided.

If any clinically significant signal is detected and need further characterization, exploration of time to onset will be performed for selected PCSAs assessed during the TEAE period as described below to account for the differential exposure time in all patients.

Kaplan-Meier curves during TEAE period will be also provided using the midpoint of the time interval between the first assessment with PCSA and the previous assessment. Only the first event (PCSA) will be counted. Patients without any event will be censored at the last assessment performed during the TEAE period.

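### Laboratory PCSA Kaplan-Meier curves continue past Week 24 on a small, selectively re-sampled risk set, so any late first PCSA gives a disproportionately large step

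*SAP*

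**What the plan says.** **The curve.** SAP 2.4.5.3 makes the analysis conditional: "If any clinically significant signal is detected and need further characterization, exploration of time to onset will be performed for selected PCSAs". Events are dated "using the midpoint of the time interval between the first assessment with PCSA and the previous assessment", and "Only the first event (PCSA) will be counted". For everyone else, "Patients without any event will be censored at the last assessment performed during the TEAE period". SAP 2.1.4 (Observation period) sets the end of the TEAE period at 70 days after the last double-blind injection.

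**The sampling.** Hematology, chemistry and CPK are scheduled for all patients at Weeks 12 and 24, and the liver panel at Weeks 4, 8, 12, 16 and 24. Week 32 is different. Footnote a of the flow chart (Protocol 1.2) marks these tests "To be obtained at the follow up visit only in case of clinically relevant abnormal values for these parameters". Protocol 10.1.3.1 repeats it: "Only in case of clinically relevant abnormal values for these parameters at the end of treatment visit will the following be obtained at this visit". SAP 2.1.4.3 agrees, placing this sampling "during the follow-up visit (Visit 9 [Week 32]) in case of abnormality".

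**Extra samples.** Protocol section 10 asks for an immediate recheck of any clinically relevant abnormal laboratory value. SAP 2.4.5 counts unscheduled and repeat evaluations in the TEAE period towards PCSAs.

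**Vital signs.** SAP 2.4.5.4 uses the same midpoint and censoring rules, but vital signs are taken from every patient at Week 32.

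**The concern.** Kaplan-Meier estimation needs censored patients to have the same later risk as those still followed. Here, whether a completer is followed after Week 24 depends on the Week 24 laboratory result: normal means censored, abnormal means re-sampled. The rule suits vital signs, but it was carried over to laboratory tests without allowing for their selective Week 32 schedule. Neither document stops the laboratory curve at Week 24 or sets a minimum number at risk.

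The curves are called for once a laboratory signal has been seen, to describe its time to onset. A large late step could then be read as delayed toxicity during the residual-effect period, or as a difference between arms, when it mostly reflects who was re-sampled. The ezetimibe arm is half the size, so a single event moves its curve further.

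**Working it through.** **1. Timing (from the documents).** The last injection is at Week 22 (Protocol 8.1.2): Day 1 + 22×7 = 155. The TEAE period ends on Day 155 + 70 = 225. The Week 32 visit is Day 1 + 32×7 = 225. This agrees with Protocol section 4, which puts the follow-up visit 10 weeks after last dosing.

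**2. Where events are plotted.**
- First PCSA at Week 24, previous sample at Week 12: (85 + 169)/2 = Day 127.
- First PCSA at Week 24, liver panel with previous sample at Week 16: (113 + 169)/2 = Day 141.
- First PCSA at Week 32: (169 + 225)/2 = Day 197.

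Event-free patients who are normal at Week 24 are censored at about Day 169, before Day 197. A patient with a PCSA at Week 24 has already had the event and cannot add a later step.

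**3. Visit window.** Week 32 ± 7 days covers Days 218 to 232. With the TEAE period ending on Day 225, 8 of those 15 days fall inside it. With the last injection 3 days early or late, 5 or 11 of the 15 do.

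**4. Step size.** After Week 24 the estimate is F = 1 − S24 × (1 − e/R). S24 is the event-free proportion at Week 24, R the number of event-free patients re-sampled, and e the number of new first PCSAs. Assumptions not in the documents: S24 = 0.95; 2%, 5% or 10% of event-free patients re-sampled; e = 1.

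| Arm | Event-free at Week 24 | R | F | F if all were sampled |
|---|---|---|---|---|
| 400 | 380 | 8 | 1 − 0.95×7/8 = 16.9% | 1 − 0.95×379/380 = 5.25% |
| 400 | 380 | 19 | 1 − 0.95×18/19 = 10.0% | 5.25% |
| 400 | 380 | 38 | 1 − 0.95×37/38 = 7.5% | 5.25% |
| 200 | 190 | 4 | 1 − 0.95×3/4 = 28.8% | 1 − 0.95×189/190 = 5.5% |
| 200 | 190 | 10 | 1 − 0.95×9/10 = 14.5% | 5.5% |
| 200 | 190 | 19 | 1 − 0.95×18/19 = 10.0% | 5.5% |

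With e = 0, F stays at 5.0% in every row.

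**5. Sensitivity to what triggers re-sampling (simulation, all inputs assumed).**
- One normally distributed marker, within-patient correlation 0.5 to 0.9, PCSA threshold at 1.645 or 2.05 SD. If the clinically relevant threshold is 0.2 or 0.45 SD looser than the PCSA threshold, the Week 32 estimate is 11-25%, against 3-12% with full sampling. If the two thresholds coincide and only that marker triggers re-sampling, R = 0 and there is no step.
- PCSA as the top 2%, clinically relevant as the top 5%, correlation 0.5 to 0.7. The mean estimate is about 11-14% against about 4.4-5.1%. However, there is no late step in roughly a third to two fifths of 400-patient arms and about three fifths of 200-patient arms.
- The same setting, with a further 10-20% of patients re-sampled because of another parameter in the panel. The mean falls to about 5.4-6.4%, against 4.4-5.2% with full sampling.

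**The case against.** A reader might infer that the curve must jump after Week 24. The documents do not support that. A step needs a patient who has had no PCSA through Week 24, is sampled again, and then has a first PCSA within the TEAE period. Otherwise the curve is flat.

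Other points on the other side:

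- **Direction and size depend on an undefined term.** The documents do not say how a clinically relevant abnormality relates to the PCSA limits. PCSAs are themselves values the sponsor regards as medically important. If the thresholds coincide, nobody re-sampled for that marker alone is still at risk for it. This stands, and it is why no single percentage should be quoted as the bias.
- **Panels.** Protocol 10.1.3.1 lists whole panels. If they are drawn whole, a patient recalled for one chemistry value is back at risk for the others, and the mean excess can shrink to about one or two points. This also stands. For those parameters the late segment is mainly unstable.
- **Visit window.** Some Week 32 samples fall outside the TEAE period. That makes steps rarer, but it thins the risk set further and does not remove the selection.
- **Residual-effect period.** The SAP includes these weeks deliberately, and cutting the curve removes them from it. The TEAE-period incidence table still covers them.
- **Status.** The curves appear only if a signal is found, and safety reporting is descriptive with no inferential testing. This stands and limits the severity.
- **Early discontinuers.** They are asked to keep the routine visits (Protocol 10.3.4), so the problem concerns patients who complete treatment.

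**Conclusion.** The point holds in limited form. For completers, the laboratory PCSA curve after about Day 169 rests on a small group selected by their laboratory results. Any first PCSA found there gives a disproportionately large step, so the late segment and any comparison of arms on it should not be interpreted. The timing and the censoring mechanism follow from the documents alone. The percentages depend on assumed event rates and re-sampling shares. Upward bias is expected when the same or a related parameter triggered the re-sampling and the trigger is looser than the PCSA limit. Otherwise the problem is instability, or there is no step at all.

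Severity is minor. The PCSA incidence tables, the vital-sign curves and all efficacy analyses are unaffected.

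**What to change.** In SAP 2.4.5.3, state that the laboratory PCSA Kaplan-Meier curves end at each patient's scheduled Week 24 sample, the last one planned for everyone, or at the end of that patient's TEAE period if earlier. Censor event-free patients at their last assessment up to that point, and show numbers at risk under the curves. List separately any first PCSA found only on a later recheck or a selective Week 32 sample.

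The cut should be at the scheduled sample and not at Day 182, the end of the Week 24 analysis window in SAP Table 2. Between about Day 169 and Day 182 normal patients are already censored, while abnormal ones may be rechecked, so the same selection would remain.

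Keep the TEAE-period PCSA incidence table and the vital-sign curves in 2.4.5.4 as they are. Visits, sampling and patient management do not change.

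The cost is a sentence or two in the SAP. The downside is that late first PCSAs move from an exploratory curve to a listing; they stay in the incidence table.

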### ***Hepatitis C antibody***

The number and percentage of patients with a post-baseline seroconversion for hepatitis C test will be provided by treatment group in post-baseline (including the TEAE and post TEAE periods) as well as in the TEAE period alone. Post-baseline seroconversion is defined for patients with a negative baseline status who had either a “positive ribonucleic acid” (RNA) or a “confirmed positive antibody with negative RNA” post-baseline status as defined in the table below. Other situations require case by case evaluation and will be described individually if relevant.

The status as regards to hepatitis C virus (HCV) for a patient will be defined as follows for all evaluations (baseline and post-baseline).

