 - Any clinically significant abnormality identified at the time of screening that in the judgment of the Investigator or any Subinvestigator would preclude safe completion of the study or constrain endpoints assessment such as major systemic diseases, patients with short life expectancy.
 - Considered by the Investigator or any Subinvestigator as inappropriate for this study for any reason, eg:
 - Deemed unable to meet specific protocol requirements, such as scheduled visits

- Deemed unable to administer or tolerate long-term injections as per the patient or the investigator
- Investigator or any Subinvestigator, pharmacist, study coordinator, other study staff or relative thereof directly involved in the conduct of the protocol, etc
- Presence of any other conditions (eg, geographic, social) actual or anticipated, that the Investigator feels would restrict or limit the patient's participation for the duration of the study

- E 32. Laboratory findings during the screening period (not including randomization Week 0 labs):
- Positive test for Hepatitis B surface antigen or Hepatitis C antibody (confirmed by reflexive testing)
 - Positive serum beta-hCG or urine pregnancy test (including Week 0) in women of childbearing potential
 - Triglycerides >400 mg/dL (>4.52 mmol/L) (1 repeat lab is allowed)
 - eGFR <30 mL/min/1.73 m²
 - ALT or AST >3 x ULN (1 repeat lab is allowed)
 - CPK >3 x ULN (1 repeat lab is allowed)
 - TSH $<LLN$ or $>ULN$ (1 repeat lab is allowed)

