**Table 1 - Definition of the patient status regarding hepatitis C virus**

	Hepatitis C Antibody (Ab) test result				
	Negative		Positive		
Reflexive test a – hepatitis C RNA test	Not available or HCV RNA not detected	HCV RNA detected	HCV RNA not detected b	HCV RNA detected	Not available
Hepatitis C status - label	Negative	Positive RNA	Negative b	Positive RNA	Positive Ab – no RNA available

*a* Test performed at the same time or after the antibody test in the pre-treatment period (for baseline evaluation), or post-baseline, respectively

*b* For post-baseline evaluation, a second antibody test with a different type of assay is to be done at the same date or after the first antibody test. The result of this test will modify the final hepatitis C status of the patient in some cases (see details in the text below the table)

The baseline evaluation will be based on tests performed during the pre-treatment period.

In case of multiple hepatitis C tests available for the post-baseline evaluation, the positive status of the patient will be defined as follows:

- “Positive” status if at least one post-baseline positive RNA is detected, regardless of status of the patient at the end of treatment.
- Else “Positive Ab – no RNA available” status if no post-baseline reflexive RNA test is available for at least one post-baseline positive antibody test.

If no antibody test is available or with “indeterminate” as result pre-treatment or post-baseline, respectively, the RNA test (if available) will be used alone to determine the status of the patient. If no RNA is available then the hepatitis C status of the patient will be missing.

The post-baseline status “confirmed positive antibody with negative RNA” will replace “Negative” status as defined above in the case where no RNA was detected post-baseline and the 2 antibody tests surrounding the same visit (from 2 different types of assay) are positive.

For a conservative approach, the post-baseline status “Positive Ab – no RNA available” will not be modified by the availability of a second antibody test from a different assay.

For the description of the positive hepatitis C virus test during the TEAE period, all above rules applied by replacing post-baseline by TEAE period.

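### The SAP's hepatitis C seroconversion definition counts an unchanged antibody-positive, RNA-negative patient as a new seroconversion when an RNA test was done before treatment

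*SAP*

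**What the plan says.** The protocol (11.4.3.2) promises the number and percentage of patients with an observed hepatitis C seroconversion by treatment group and leaves the definition to the SAP. SAP 2.4.5.3 (Hepatitis C antibody) supplies it: "Post-baseline seroconversion is defined for patients with a negative baseline status who had either a" *positive RNA* status or a *confirmed positive antibody with negative RNA* status after baseline. The count is reported twice, once over the whole post-baseline period and once for the TEAE period.

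The status comes from SAP Table 1, which "will be defined as follows for all evaluations (baseline and post-baseline"). In the row headed "Hepatitis C status - label", a positive antibody with RNA not detected is labelled *Negative*, the same label that an antibody-negative patient receives.

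Table 1 footnote b then adds a step on one side only: "For post-baseline evaluation, a second antibody test with a different type of assay is to be done". The text below the table gives the consequence: "The post-baseline status “confirmed positive antibody with negative RNA” will replace “Negative” status as defined above". This applies when no RNA is found after baseline and "the 2 antibody tests surrounding the same visit (from 2 different types of assay) are positive".

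On entry, protocol 7.2.1 criterion E32 lists as an exclusion a "Positive test for Hepatitis B surface antigen or Hepatitis C antibody (confirmed by reflexive testing").

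**The concern.** The definition starts from a status label, not from an antibody result. The label *Negative* hides whether the baseline antibody was negative or positive. After baseline the hidden part is brought out, because a second assay can turn the same pair of results into a status that counts as an event. A patient with long-standing antibody and no virus could then be reported as having seroconverted on study because an extra assay was run, with no change in any result.

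What is at stake is the reading of a pre-specified safety table. A reader of the study report would take each counted patient as newly antibody-positive or newly infected during the trial. Efficacy analyses are not touched.

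**Working it through.** The documents state no figure on this point, so there is none to reproduce. The check is to apply the rule to every combination of results.

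**Inputs (SAP 2.4.5.3, Table 1, footnotes a and b, and the text below the table)**

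| Antibody | RNA | Baseline status | Post-baseline status |
|---|---|---|---|
| Negative | Not detected or not available | Negative | Negative |
| Negative | Detected | Positive RNA | Positive RNA |
| Positive | Not detected, second assay not positive | Negative | Negative |
| Positive | Not detected, second assay positive | Negative (no second assay is specified at baseline) | Confirmed positive antibody with negative RNA |
| Positive | Detected | Positive RNA | Positive RNA |
| Positive | Not available | Positive Ab – no RNA available | Positive Ab – no RNA available |

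A patient is counted if the baseline status is *Negative* and the post-baseline status is *Positive RNA* or *Confirmed positive antibody with negative RNA*.

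**Result of the enumeration.** With a definite antibody result at each end, nine combinations are counted.

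1. Six start from a negative baseline antibody. In each of them either the antibody or the RNA result has changed.
2. Two start from a positive baseline antibody with RNA not detected and end with RNA detected. Something has changed in these too.
3. One starts from a positive baseline antibody with RNA not detected and ends with the same two results plus a positive second assay. Nothing has changed, and it is still counted.

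The third group is the fault. If the second assay is negative, the status stays *Negative* and the patient is not counted. If there is no baseline RNA result, the baseline status is *Positive Ab – no RNA available* and the patient is not counted.

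**A related route.** The SAP also says that if the pre-treatment antibody result is missing or indeterminate, the RNA test alone sets the status. Such a patient with RNA not detected is *Negative* at baseline. A confirmed antibody at Week 24 is then counted, although no change in antibody can be shown.

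**Can the unchanged patient be in the trial with a baseline RNA result?** The documents point both ways.

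- *Yes:* E32 makes exclusion depend on reflexive testing in the screening period. Table 1 names the reflexive test as the RNA test, and footnote a provides for it in the pre-treatment period for the baseline evaluation. If E32 means that test, an antibody-positive, RNA-negative patient is not excluded by it.
- *No:* protocol Section 10 (Laboratory tests) places reflexive testing of a positive hepatitis C antibody at the end of treatment only. Flow chart footnote i (Section 1.2) ties the confirmatory test to Week 24. Section 10.1.2.5 adds automatic confirmation at Week 24, and the screening list in 10.1.1.1 has no such wording.

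**Size.** The documents give no prevalence. Assume that 0.5% to 2% of randomized patients are antibody-positive and RNA-negative at screening, and that all of them have Week 24 tests and a positive second assay:

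- Total: 600 × 0.005 = 3, and 600 × 0.02 = 12.
- Alirocumab: 400 × 0.005 = 2, and 400 × 0.02 = 8.
- Ezetimibe: 200 × 0.005 = 1, and 200 × 0.02 = 4.
- As a percentage of each arm: 0.5% to 2% in both.

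These are upper figures for the assumed range, because any patient without a Week 24 sample or with a negative second assay drops out.

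**The case against.** The strongest objection is that the path may never be reached. If Section 10, footnote i and Section 10.1.2.5 describe what is done, no RNA test is run at screening. Every enrolled antibody-positive patient is then *Positive Ab – no RNA available* at baseline and cannot enter the count. This stands as a condition on the point. It does not clear the rule, because footnote a expressly provides for a pre-treatment RNA test, and that is the case in which the rule miscounts.

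Secondly, E32 does not say what its reflexive test is. If confirmation at screening included a second antibody assay, patients with genuine old antibody would be excluded, and they are the ones expected to pass the second assay at Week 24. The SAP's row label supports the RNA reading but does not settle it. This also stands.

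Thirdly, the SAP sends other situations to case-by-case review. That does not help, since the clause covers cases outside the definition and this patient meets the definition exactly. The second assay does not help either. It removes false-positive first tests, but a true old antibody would be expected to be positive on both.

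Fourthly, the table is descriptive with no formal testing, and hepatitis C seroconversion is not among the adverse events of special interest. The error can only add patients, and each can be checked against the antibody result collected at screening. All of this is right and keeps the severity low.

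**Conclusion.** The definition is wrong as written. Where a pre-treatment RNA result exists, a patient with unchanged antibody-positive, RNA-negative results and a positive second assay is counted as a seroconversion. Severity is low. Confidence is moderate, because whether that RNA result exists depends on protocol passages that contradict each other.

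Under the assumed 0.5% to 2%, at most 3 to 12 of 600 patients would be falsely counted. The true prevalence, and so the true size, is unknown from the documents.

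A reader might infer three stronger things, none of which the documents support:

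- *That false counts are certain.* They depend on a screening RNA test, on E32 admitting such patients, and on a positive second assay.
- *That the fault works against alirocumab.* With 2:1 allocation about two thirds of the false counts would fall in that arm, but that only reflects its size. The expected percentage is the same in both arms.
- *That artefacts would make up most of the table.* The documents give neither the expected number of genuine new infections nor the prevalence of old antibody.

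**What to change.** In SAP 2.4.5.3, change the antibody route only:

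- Count *confirmed positive antibody with negative RNA* as seroconversion only in patients with a documented negative baseline hepatitis C antibody result.
- Leave the *positive RNA* route as it is for every patient with a negative baseline status.
- Describe individually any patient with a positive, missing or indeterminate baseline antibody who reaches the confirmed-antibody status.

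In the enumeration this removes the one unchanged path and keeps the other eight. Restricting the whole definition to antibody-negative patients would go too far. It would drop newly detected RNA in patients whose baseline antibody was missing or indeterminate, and in those who were antibody-positive and RNA-negative at baseline.

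Separately, reconcile E32 and Table 1 footnote a with protocol Section 10, flow chart footnote i and Section 10.1.2.5 on whether a positive screening antibody is followed by reflexive testing, and state which test that is.

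The cost of the SAP change is one sentence. No new data are needed, because the screening antibody result is already collected.
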